C.3.a.2. Pharmacokinetics: Dutasteride has complex elimination kinetics (Gisleskog et al. 1999). Single doses of 0.5-5 mg are metabolized with a 3-4 day half-life, while drug accumulation following repeated doses produces delayed elimination with a half-life of weeks due to saturation of the rapid elimination pathway. The recommended daily dose for the treatment of benign prostatic hypertrophy in elderly men is 0.5 mg. The planned 4 mg loading dose, which was used as a single dose in our study of dutasteride paired with acute alcohol (C.1.a), and as a loading dose prior to 1 mg daily in a pilot study (C.1.c) is expected to produce an initial Cmax of 13-28 ng/ml [GlaxoSmithKline Phase I pharmacokinetic studies ARIA 1001 and (Gisleskog et al. 1998)], which is similar to the dutasteride blood level after 0.5 mg daily for 4 weeks (22 ng/ml, GSK Phase I pharmacokinetic studies ARIA 1003). This modest loading dose together with a daily dose of 1 mg dutasteride is expected to achieve a >90% inhibition of peripheral type II 5AR within 3 days and a 60% reduction in type I 5AR by 4 weeks for a total reduction of DHT of \approx 85% by 4 weeks (Gisleskog et al. 1998). Following discontinuation of study medication after 12-weeks, pharmacokinetic modeling suggests type I 5AR levels will return to normal \approx 4-8 weeks later with a more prolonged recovery of type II 5AR (Gisleskog et al. 1998).

C.3.a.3. Dutasteride Adverse Effects Profile: Based on extensive clinical studies in men, dutasteride is well tolerated (Avodart, Prescribing information 2006, GlaxoSmithKline). In a series of three 2-year long treatment trials including 4,300 men aged 47-94 years (mean = 66 years), 0.5 mg of dutasteride daily for treatment of prostatic hypertrophy resulted in the following adverse effects compared with placebo: impotence (4.7% vs. 1.7%), decreased sex drive (3.0% vs. 1.4%), problems with ejaculation (1.4% vs. 0.5%), and development of

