At the end of treatment week 12 (visit 8), subjects will complete a packet of questionnaires and be interviewed by research staff concerning their alcohol consumption and alcohol-related symptomatology (using the Alcohol section of the SCID-I, modified to ask about the past 30 days). Subjects will be compensated \$50 for this end-of-treatment visit. Subjects requesting additional treatment for alcohol problems will be referred to local treatment centers. For subjects who withdraw early and do not wish to continue with study visits/procedures, all end-of-treatment procedures will be administered at the time of withdrawal. Such subjects will also be invited to participate in-person or by telephone to provide Timeline Followback data at 2, 4, and 6-months post-treatment.

C.4.d. Visit 9, 10, and 11 (Post-treatment Assessment Visits): To evaluate the durability of treatment effects, patients will return to the clinic for post-treatment assessments 2,4, and 6-months after completion (or for early terminators, scheduled completion) of treatment. We will attempt to reach all subjects directly or via their locator. At this visit, the subject will complete the self-report packet of questionnaires and will be interviewed by the research staff. Blood samples for measurement of serum GGT, %dCDT and 3 α -diolG will be obtained. Subjects will be paid \$50 for the two and four month post treatment visit and \$75 for the six month post-treatment assessment visits. Subjects will be eligible to request drug assignment information after their 6-month post-treatment assessment.

C.5. Medical Management: The physician will meet with the subject at the beginning of treatment and will consult at least weekly with the study staff to monitor potential study related side effects and adverse event occurrence. The physician will evaluate the subject should severe or persistent adverse effects occur. At each treatment visit (2-7) subjects will receive brief counseling as part of medical management, which is described in detail below.

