drinking, and has been recommended as an alternative or to complement GGT measurement (Myrick et al. 2001). Serum 3 α -diolG will be measured using a commercial ELISA kit as a biochemical measure of 5AR inhibition by dutasteride. Serum testosterone will be measured using an Immulite 1000 instrument in the CRC lab to monitor for any unexpected negative effects of dutasteride on testosterone in heavy drinkers. Additional blood samples will be obtained at midpoint, end of the 12-week treatment phase and at the two follow-up visits to assay GGT, %dCDT, 3 α -diolG and testosterone. Weight, blood pressure and pulse will be obtained at each treatment visit. Additional research laboratory testing: A portion of the blood samples collected will be processed and stored for later analysis of biological correlates (including RNA) of dutasteride medication effects or of change in alcohol consumption.

C.6.b. Psychological/Behavioral Assessments: The assessments listed below were chosen because they: a) are standard, widely used assessments to maximize comparability of findings with prior treatment studies of alcohol dependence and problem drinking, b) measure multiple outcome criteria, since a reduction in drinking may or may not result in improvement in other domains, and c) assess for potential change in depression or anxiety related to treatment as additional safety measures.

C.6.b.1. Areas assessed only at Visit 1 (in person screening):

a. *Sociodemographic patient information:* Medical history, family history of alcoholism, marital status, educational and occupational information and substance abuse treatment history.

b. *Locator information:* Study staff will identify subject locators on the basis of relationship to client, duration and current status of relationship, frequency of contact with the subject, and willingness to participate. Locators are contacted when efforts to reach a subject are unsuccessful, which contributes both to maintaining subjects in treatment and data collection.

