c. *Psychiatric diagnosis:* The Structured Clinical Interview for DSM-IV (SCID-I/P) (First et al. 1997) will be used to classify subjects according to the presence or absence of major psychiatric disorders including AD. This, together with the physician's unstructured psychiatric interview (visit 2), will be used to assess exclusion criteria for serious psychiatric disorders. The SCID-I/P will be administered at screening visit and the alcohol portion of the SCID will be administered at treatment end-point and the 2, 4, and 6-month follow-up visits to evaluate presence of current alcohol dependence criteria after treatment.

d. *Family history of alcohol dependence:* This interview systematically questions an informant about the presence of psychiatric illness in relatives. We will use the alcohol section of the Family History Assessment Module FHAM (Rice et al. 1995) the subject will be asked to provide information concerning his biological relatives history of alcohol use, however, names of family members will not be obtained.

Table 1: Schedule of Assessments

Study Visit	V 1 Screening	V 2 Baseline	Bi-weekly phone call	V 3-7	V 8 End-point	V 9: 2-mo follow-up	V 10: 4-mo follow-up	V 11: 6- mo follow-up
Time relative to Medication		Start medication	wks 1,3,5	wks 2, 4,6,8,10	Wk 12 End medication			
Medical History, SCID, Fam Hx, Clinical lab tests, blood for DNA	X							
Timeline Follow-Back Interview	X	X		X	X	X	X	X
Vital signs & weight	X	X		X	X			
Alcohol Effects Questionnaire	X				X		X	X
Study outcome blood samples	X			wk 6	X	X	X	X
Physical Exam & Clinician review of Medical History		X						
Penn Alcohol Craving Scale (PACS)		X		X	X	X	X	X
SIP, DMQ, BDI, STAI		X		wk 6	X	X	X	X

Daily IVR call		X	X	X	X			
Side Effect Checklist			X	X	X	X		
Medical Management		X		X				
MED-Q					X			
Follow-up Interview (Alcohol SCID)					X	X	X	X

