d. *Daily Events:* Participants will be asked whether they experienced a list of nine possible daily events (3 stressful, 3 pleasant, and 3 situations where someone might drink). These measures will be used to assess the influence of positive and negative events on drinking.

e. *Daily medication usage:* Using IVR, subjects will report daily medication use. Additionally, at each bi-weekly study visit, subjects will be asked by the study staff to indicate the number of study drug capsules taken each day. This method has been shown to be highly correlated with electronic monitoring of medication adherence (Feinn et al. 2003).

C.6.b.3. Areas assessed biweekly during the active treatment period and follow up visits:

a. *Alcohol use patterns:* The TLFB (Sobell and Sobell 1992) will be used to estimate drinking at intake, at each biweekly study visit during the active treatment period and at each of the two follow-up evaluations. This interview procedure will provide quantity/frequency of alcohol consumption data for each day during the period prior to the interview. We will also be collecting daily measures of alcohol consumption using IVR during the active treatment period because despite evidence of the reliability and validity of the TLFB when used by trained interviewers, the TLFB is less useful for detecting patterns of alcohol consumption that vary on a day-to-day basis (Carney et al. 1998; Searles et al. 2000). Daily IVR reports will also enable us to examine co-variation in daily mood and daily events with alcohol use in order to address whether dutasteride moderates associations between daily mood or daily events and drinking as our group has found using IVR methods for treatment with naltrexone (Kranzler et al. 2004; Armeli et al. 2006).

b. *Alcohol Craving:* The Penn Alcohol Craving Scale (PACS) is a 5-item self-report measure that includes questions regarding the frequency, intensity, and duration of craving over the past week as well (Flannery et al., 1999). The PACS has been shown to predict subsequent drinking during alcohol treatment trials (Flannery et al., 1999, 2003).

c. *Medication adverse effects:* Subjects will provide reports of side effects at each bi-weekly phone visit and study visit during the active treatment phase and 2-month follow-up visit using a list of adverse medication

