effects derived from prior studies of dutasteride (any ongoing potential medication side effects reported at the 2-month follow-up will be assessed again at 4- and 6-month follow-up visits as needed).

d. Measures of treatment received: Records of all medication taken will be recorded. The study staff will also record the number of contact hours subjects have been exposed to for any treatment outside of the study that is related to their drinking to identify if this variable might need to be considered as a covariate in outcomes analysis.

C.6.b.4. Areas assessed at intake, midpoint, end of treatment and at follow-up visits:

a. Alcohol-related problems: The Short Inventory of Problems (SIP). The SIP is a 15-item instrument derived from the Drinker Inventory of Consequences (DrInC), which was developed for use in Project MATCH as a measure of alcohol-related consequences.

b. Psychological symptoms: a) The Beck Depression Inventory (BDI), a 21-item self-report measure of depressive symptoms, yields a total score that ranges from 0 to 63 (Beck et al. 1961). The BDI is generally regarded as a sensitive self-report measure of depressive symptoms, and will be used to explore the relation between depressive symptoms and treatment. b) The State version of the Spielberger State-Trait Anxiety Inventory (STA), a 20-item self-report questionnaire (Spielberger 1983), will be used to provide concomitant monitoring of anxiety symptoms.

c. Drinking Motives: Drinking motives will be measured with the Drinking Motives Questionnaire [DMQ; (Cooper et al. 1992; Cooper 1994)] to explore potential changes as a result of treatment in drinking motives. This instrument contains 20 items with 4 subscales, drink to a) cope motives (e.g., "Because it helps when you are feeling nervous or depressed"), b) conformity motives (e.g., "Because it helps me fit in"), c) enhancement motives (e.g., "Because it's fun"), and d) social motives (e.g., "Because it makes a social occasion more enjoyable"). The DMQ will be administered at baseline and for those subjects who continue to drink again at midpoint, end of treatment and at the 2,4, and 6-month follow-up visits.

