E.7. Comparison of risks and anticipated benefits to patients and society: The risks associated with the counseling are minimal. Although the medication presents some risk, it has been shown to be safe when administered for benign prostatic hypertrophy for long periods of time (years). The potential risks of these treatments are minor compared to the risk incurred by individuals who continue to drink heavily. The risk/benefit ratio thus appears favorable to the proposed treatments.

E.8. Data and Safety Monitoring Plan (DSMP): The DSMP is established to ensure the safety of research participants and the integrity of the study data. [name], M.D., the principal investigator of this study, or one of the other study physicians, will be charged with the duty of determining the severity rating of adverse events. The study staff (P.I., co-investigators, clinical research coordinator) are responsible for collecting and recording all clinical data. As these results are collected, all toxicities and adverse events will be identified, graded for severity and assigned causality, reported to the required entities, and compiled for periodic review. After assigning causality, the P.I. will decide the course of action for the study participant. The P.I. will evaluate every adverse event and determine whether it affects the risk/benefit ratio of the study and whether modifications to the protocol or informed consent form are required. The principal investigator (and, in his absence, physician co-investigators) will differentiate serious from non-serious adverse events. Serious adverse events that are related to the study interventions and unexpected will be reported to the UCHC IRB and the NIAAA project officer within 48 hours. An annual report summarizing all adverse events will be prepared and reported to the NIAAA project officer. The following information will be considered in the periodic safety report:

- Number of patients who have completed the study.
- Dropout rates and reasons for the dropouts.
- Summary of adverse events.
- Any other relevant information

Adverse events during the treatment will be reported to the UCHC IRB, as well as to the NIAAA on an annual basis, with serious adverse events that are related to the study interventions and unexpected being reported within 48 hours. Any patients thought to be at risk from drinking or psychiatric or medical disorders during

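### Side effects that first appear after the 2-month follow-up visit have no scheduled collection, and the adverse-event reporting window is stated inconsistently

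*Combined protocol and SAP*

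**What the plan says.** **Collection.** Section C.6.b.3.c states: "Subjects will provide reports of side effects at each bi-weekly phone visit and study visit during the active treatment phase and 2-month follow-up visit". It adds that "any ongoing potential medication side effects reported at the 2-month follow-up will be assessed again at 4- and 6-month follow-up visits as needed". Table 1 agrees: the row "Side Effect Checklist" is marked for the phone calls, V3-7, V8 and V9, and is blank for V10 and V11.

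**Early withdrawal.** Under C.4.c, men who withdraw and do not want further visits have the end-of-treatment procedures when they leave. Then: "Such subjects will also be invited to participate in-person or by telephone to provide Timeline Followback data at 2, 4, and 6-months post-treatment".

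**Reporting.** One sentence of E.8 reads: "Adverse events during the treatment will be reported to the UCHC IRB, as well as to the NIAAA on an annual basis". Another in the same section reads: "An annual report summarizing all adverse events will be prepared and reported to the NIAAA project officer". The 48-hour rule for related, unexpected serious events carries no time limit.

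**Pharmacology.** Section C.3.a.2 expects type I 5AR to be back to normal about 4-8 weeks after the last dose, "with a more prolonged recovery of type II 5AR". It gives no duration for type II.

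**What runs to 6 months.** Drinking is analysed over the whole follow-up (Aim 2, C.8.a.2). Section C.4.d and Table 1 place blood draws, including the inhibition marker 3-alpha-diolG, at V9, V10 and V11.

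**The concern.** Aim 1 is a safety aim as well as an efficacy aim. The adverse effects listed in C.3.a.3 are sexual and breast effects, and C.3.a.1 describes type II 5AR as the main form in the prostate and the source of two-thirds of circulating DHT. If type II inhibition lasts beyond V9, there is a period in which the drug may still be acting and no scheduled question asks about new effects. The plan would then have data on persisting benefit and persisting inhibition for those months, but nothing systematic on new harm.

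The analysis section does not resolve this. C.8.a.1 compares adverse events between arms without stating the period over which they are counted, and E.8 can be read in two ways. Two analysts could draw up different event tables from the same protocol.

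**Working it through.** The plan gives no figure on this point to reproduce. The check sets the schedule against the other sections and converts visit times to weeks.

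**1. Visit times.** Weeks = months × 365.25 / 12 / 7.

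| Visit | Weeks after treatment | Checklist | TLFB and outcome bloods |
|---|---|---|---|
| V8 | 0 | every man | yes |
| V9 (2 months) | 8.7 | every man | yes |
| V10 (4 months) | 17.4 | only effects ongoing at V9 | yes |
| V11 (6 months) | 26.1 | only effects ongoing at V9 | yes |

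Interval with no scheduled question on new effects: 26.1 − 8.7 = 17.4 weeks. Share of follow-up: (6 − 2) / 6 = 67%.

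**2. Against the stated enzyme recovery.** Type I recovery (about 4-8 weeks) ends just before V9 at 8.7 weeks. Only type II recovery could run past V9. It is described as slower than type I, with no duration, so how much of the 17.4 weeks it covers cannot be calculated.

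**3. Men who withdraw and decline visits.** C.4.d counts follow-up for early terminators from scheduled completion. Assuming the TLFB contacts in C.4.c use the same clock:

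weeks from last dose to first contact = (12 − stop week) + 8.7

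- Stop at week 2: 10 + 8.7 = 18.7 weeks.
- Stop at week 6: 6 + 8.7 = 14.7 weeks.

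If the contacts were instead counted from withdrawal, the interval would be 8.7 weeks in each case. On either clock no side-effect question is specified. These men do have the checklist at withdrawal, because Table 1 marks it at V8 and C.4.c applies the end-of-treatment procedures to them.

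**4. Reporting window in E.8.** Three statements stand together: annual reporting of events in the treatment period, an annual summary of all adverse events, and the 48-hour rule. Only the first has a time limit, so a post-treatment event falls outside the first and inside the second.

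**5. Testosterone.** C.4.c lists it among the study outcome measures, and Table 1 marks study outcome bloods at V9, V10 and V11. C.6.a has samples at the "end of the 12-week treatment phase and at the two follow-up visits to assay GGT" and other analytes, testosterone among them. C.4.d omits testosterone from the follow-up draw. C.6.a also counts two follow-up visits where C.4.d and Table 1 have three.

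**The case against.** The strongest case against the point is that this is a deliberate choice. Aim 1 concerns tolerability of a 12-week treatment. Asking to 2 months and then tracking unresolved complaints is a recognisable scheme, and nothing in the protocol requires solicited safety questions to last as long as the drinking follow-up. The V9 checklist can also ask about the type I recovery period that has just closed, though by recall over 8.7 weeks. This stands in part: the choice is defensible, but the protocol gives no reason for stopping at V9, and its own expectation for type II makes the later period relevant.

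Several stronger readings are tempting, and the documents do not support them.

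- *Side effects cease to be asked about at 2 months.* Ongoing ones are carried to V10 and V11; only new onsets are missed.
- *Post-treatment events are neither collected nor reported.* E.8 has open-ended provisions for all adverse events and for related, unexpected serious ones. It also provides for referral of men at risk during follow-up. The BDI and STAI, called additional safety measures in C.6.b, continue to V11, and E.5 gives men emergency contact numbers.
- *All early withdrawers get drinking questions alone.* The TLFB-only offer is for men who decline further visits. C.8.a.2 follows men whether or not they stay on treatment, and C.4.d includes early terminators in the clinic visits.
- *Nine per cent of men are affected.* The 16 of 176 (176 − 160) are those expected not to complete treatment. How many of them would also decline visits is not given.
- *The tolerability comparison is too favourable.* No bias is demonstrated. Discontinuation due to adverse events is itself a planned comparison, and in the pilot none of the three dropouts left because of side effects.
- *Testosterone is not assayed at follow-up.* Most of the text implies that it is. The fault is conflicting wording.

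**Conclusion.** The point holds in a limited form. New side effects starting after V9 are not systematically collected for about 17.4 of 26.1 follow-up weeks, while drinking and the inhibition marker are followed to the end. The schedule and the text of C.6.b.3.c agree on this, so it is not a table error. Men who decline visits after withdrawing have no specified side-effect question once they leave; the size of that group is unknown. The reporting sentences in E.8 are inconsistent, and C.8.a.1 does not settle which events count.

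The relevance of the gap rests on type II recovery extending past V9. The protocol makes this plausible but does not quantify it. How many events would be missed, and whether the arms would differ in them, cannot be derived from the documents. The primary efficacy analysis is untouched. This is a worthwhile, inexpensive improvement to the safety data, not a flaw that undermines the trial.

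**What to change.** 1. In Table 1 and C.6.b.3.c, give the checklist to every man at V10 and V11 as well as V9.
2. In C.4.c, add the checklist to the TLFB contacts already offered to men who withdraw, and record time since last dose.
3. In E.8, reconcile the reporting sentences to one adverse-event window that runs to the 6-month visit.
4. In C.8.a.1, state the window for the comparisons and report on-treatment and post-treatment events separately.
5. Reconcile C.4.d with C.4.c, C.6.a and Table 1 on follow-up testosterone, and correct the number of follow-up visits in C.6.a.

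The cost is a few minutes per contact at visits or calls that already take place, a short amendment, and slightly more reported events. Reporting the two periods separately keeps those extra events from blurring the on-treatment comparison.
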